## Abbreviations and Definitions

*Extension of the list of AGIL abbreviations:*

dcrit	Critical difference
ESCCA	EULAR Standing Committee for Clinical Affairs
EULAR	European League Against Rheumatism
HDL cholesterol	High-density lipoprotein cholesterol
LDL cholesterol	Low-density lipoprotein cholesterol
LOCF	Last observation carried forward
SCORE	Systematic Coronary Risk Evaluation

---

## 1 Changes to the observational plan

### 1.1 Introduction

*Introduction: AGIL-CV as a supplement to AGIL:*

Amendment I describes the collection and analysis of cardiovascular and metabolic risk parameters in patients with rheumatoid arthritis (RA) determined in the course of additional documentation to NIS AGIL.

RA patients have increased cardiovascular morbidity and mortality as compared to the overall population. Furthermore, the majority of premature deaths in RA patients are attributable to cardiovascular disease (1), (2). RA patients show a higher cardiovascular risk, which can be put down to a higher prevalence of traditional risk factors (e.g. hypertension, dyslipidemia, smoking (3) as well as the underlying systemic inflammation, which play a key role in the development and progression of arteriosclerosis (4). Markers of inflammation are independent predictors of cardiovascular death (5). The systemic inflammation may even be the key process leading to myocardial infarction and premature death (6). RA is also associated with a pro-atherogenic lipid profile: Low HDL cholesterol levels are observed, which lead to an unfavorable cholesterol ratio (total cholesterol/HDL cholesterol) (7), (8). The prevalence of cardiovascular disease in RA is increased to an extent that is comparable to that of type 2 diabetes (9). Accordingly, RA should be regarded as an independent cardiovascular risk factor, and regular cardiovascular risk screening and management is therefore needed (1).

As TNF plays a significant role in the development of inflammatory processes, the inflammatory process of arteriosclerosis may be interrupted by inhibiting this cytokine. Studies show that early initiation of effective therapy is associated with a decreased cardiovascular risk (6), (10), (11).

The Standing Committee for Clinical Affairs of the European League Against Rheumatism ([EULAR], ESCCA) thus issued evidence-based recommendations for cardiovascular risk management in patients with rheumatoid arthritis that stress the implication of adequate control of disease activity and annual examinations to assess the cardiovascular risk (1).

Rheumatologists implementing these recommendations in everyday practice can routinely record their RA patients' cardiovascular and metabolic risks using this documentation.

## 1.2 Rationale

*Rationale and considerations regarding objectives of AGIL-CV in addition to AGIL:*

This supplementary documentation serves to record cardiovascular and metabolic risk factors in RA patients prior to starting adalimumab treatment in a routine clinical setting. In addition, the course of these risk factors and the impact of the disease activity on this course are to be documented during the 60-month adalimumab treatment.

## 1.3 Research question

*Description of study aims AGIL-CV as a supplement to AGIL:*

The **primary research questions of AGIL-CV** are

- To determine baseline changes in Months 12, 24 and 60 after starting adalimumab treatment with regard to the following primary cardiovascular and metabolic parameters:
  - Lab chemistry blood parameters for glucose and lipid metabolism
  - Vital signs
  - Body measurements
- The comparison between DAS28 responders and DAS28 nonresponders in terms of the primary parameters "lab chemistry blood parameters for glucose and lipid metabolism" and "vital signs"
- Determination of the time point and frequency of cardiovascular events in the course of the entire documentation

The secondary **research question** addresses the investigation of the impact of the

---

personal data and familial medical history recorded at baseline on the previously specified cardiovascular and metabolic parameters. The Systematic Coronary Risk Evaluation (SCORE) risk model is applied to determine the individual risk and changes thereof over time.

#### **1.4 Number of patients to be included in AGIL-CV**

*Patient number required for the AGIL-CV research question in addition to AGIL*

At least N=300 RA patients are required for the study to evaluate the cardiovascular and metabolic changes. This number takes premature therapy discontinuation by 50% of patients up to Month 60 into account (see Section 1.9).

#### **1.5 Physician's selection criteria AGIL-CL**

*Additional selection criteria for the conduct of AGIL-CV:*

The data for additional documentation of cardiovascular and metabolic risk factors are collected at selected sites that determine the cardiovascular risk profile as a routine measure for monitoring RA patients. All of these sites participate in NIS AGIL.

#### **1.6 Course of long-term AGIL-CV documentation**

*Additional supplement of AGIL-CV:*

This non-interventional study (**including Amendment I**) is conducted as a single-arm, multi-center, prospective cohort study.

Table 1 "Physician's overview" is supplemented by the following sub-table that shows the process of medical documentation for AGIL-CV.

**Table 1 Physician's overview – collection of cardiovascular and metabolic risk factors**

	Month							
	0	3	6	12	24	36	48	60 
Body measurements (weight, height, waist and hip circumference) 	X	X	X	X	X	X	X	X
Familial medical history (diabetes, obesity, premature cardiovascular disease)	X							
Tobacco use	X	X	X	X	X	X	X	X
Alcohol consumption	X	X	X	X	X	X	X	X
Vital signs 	X	X	X	X	X	X	X	X
Documentation of cardiovascular events (myocardial infarction, stroke)	X	X	X	X	X	X	X	X
Laboratory parameters (fasted) 	X	X	X	X	X	X	X	X

 Month 60 or last visit

 Height is only determined at Month 0.

 Data are incorporated into the SCORE risk model.

 Glucose (serum or plasma), lipid profile (HDL cholesterol, LDL cholesterol, total cholesterol, triglycerides, CRP)

## 1.7 Description of study activities

*Description of data to be documented for AGIL-CV as a supplement to AGIL:*

### **Baseline examination (Month 0) to determine cardiovascular risk factors**

#### **Body measurements**

Weight, height

Waist and hip circumference (waist measured 5 cm above anterior superior iliac spine)

#### **Familial medical history**

Parents' medical history: Diabetes mellitus and obesity Premature cardiovascular disease in the family

#### **Tobacco and alcohol**

Tobacco use

Alcohol consumption

#### **Vital signs**

Blood pressure (in a sitting position, after 3-minute rest period)

Pulse (in a sitting position, after 3-minute rest period)

#### **Laboratory parameters**

Glucose after fasting (serum or plasma)

Lipid profile after fasting (HDL cholesterol, LDL cholesterol, total cholesterol, triglycerides)

CRP

#### **Documentation of cardiovascular events**

Myocardial infarction

Stroke

### **Examinations over the course of the study (Month 3, 6, 12, 24, 36, 48, 60) to determine cardiovascular risk factors**

Body measurements (except height)

Vital signs

Laboratory parameters

Tobacco use

Documentation of cardiovascular events

## 1.8 Calculation of CV risk model

*In addition to the documentation tools described in AGIL:*

**SCORE (Systematic Coronary Risk Evaluation):** The SCORE risk model is routinely used in European clinical practice to manage cardiovascular diseases. It permits a direct estimate of the absolute ten-year risk of fatal cardiovascular disease events. This ten-year risk calculation is based on the conditional probability of cardiovascular mortality within the next ten years, provided that the patient survives up to the index age (13).

The estimate is based on the absolute cardiovascular disease risk rather than just on the risk of coronary heart disease. The following parameters are used to calculate the score:

- Age
- Sex
- Currently smoker/non-smoker
- Systolic/diastolic blood pressure (in a sitting position, after 3-minute rest period)
- Cholesterol ratio (total cholesterol/HDL cholesterol)

The overall risk of fatal cardiovascular disease is calculated by combining two different risk estimates:

- Coronary heart disease
- Non-coronary atherosclerotic vascular disease

This calculation determines a probability score of fatal cardiovascular disease within the next ten years ranging from "< 1%" to "15% and over".

Risk models are to be modified for RA patients by applying a multiplication factor of 1.5 if a patient meets at least two of the following three criteria (1):

- Disease duration of over ten years
- Positive RF or positive anti-CCP antibody result
- Presence of certain extra-articular manifestations

### **1.9 Sample size estimation**

*Sample size estimation for AGIL-CV as a supplement to AGIL:*

The sample size estimation is based on published data concerning the blood pressure of RA patients (14):

Assuming an alpha and beta error of 5% each, the following minimum number of RA patients is required at the evaluation time points of Months 12, 24 and 60:

- N=128 patients are required in order to detect a mean systolic blood pressure difference of 10 mmHg (given a mean systolic blood pressure of 128 mmHg with a standard deviation of 18 mmHg).
- N=136 patients are required in order to detect a mean diastolic blood pressure difference of 5 mmHg (given a mean diastolic blood pressure of 74 mmHg with a standard deviation of 11 mmHg).

In documentations with adalimumab, premature discontinuation has been observed for approx. 50% of patients in the course of a 60-month documentation duration. If this rate is taken into account; an overall number of N=300 patients is sufficient to address the primary research questions given the above-named estimations.

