12.1 Sample Size Calculation

The primary parameter of this documentation is work productivity, which is captured by the number of missed working days. The sample size calculation is based on the results of an interim analysis of a documentation of adalimumab in RA with 4640 patients, of whom 1417 patients had been employed part time or full time. The mean number of missed working days was 26 days (standard deviation of 55 days) during the last 12 month prior to adalimumab therapy. The correlation between baseline and follow-up report is estimated with $r = 0.5$. According to these numbers, 850 employed patients are required to detect a mean difference of 5 days within 12 months at the 0.05 significance level (two-sided) with a power of 0.80. Since 30 % of patients are employed, a total number of about 2500 employed and non-employed patients are required in order to detect the specified difference in missed working days.

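### The AGIL-CV sample sizes of 128 (systolic) and 136 (diastolic) do not follow from one test with one correlation, and Section 1.9 states neither

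*Protocol*

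**What the plan says.** Section 1.9 of the Protocol sets alpha and beta at 5% each and says that "the following minimum number of RA patients is required at the evaluation time points of Months 12, 24 and 60". It then gives two figures:

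- "N=128 patients are required in order to detect a mean systolic blood pressure difference of 10 mmHg", with a mean of 128 mmHg and an SD of 18 mmHg.
- "N=136 patients are required in order to detect a mean diastolic blood pressure difference of 5 mmHg", with a mean of 74 mmHg and an SD of 11 mmHg.

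It adds that "premature discontinuation has been observed for approx. 50% of patients in the course of a 60-month documentation duration" and concludes that "an overall number of N=300 patients is sufficient to address the primary research questions". Section 1.4 repeats the 300 and the 50% allowance.

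Section 1.9 does not name the test, say whether one or two groups are compared, or give a correlation between baseline and follow-up blood pressure. Section 1.3 lists two primary aims to which a blood pressure difference could belong. One is "To determine baseline changes in Months 12, 24 and 60 after starting adalimumab treatment". The other is a comparison of DAS28 responders with nonresponders on laboratory values and vital signs. Section 1.10 gives stepwise regression on the changes, with DAS28 response as a coded variable, and a general linear model for the responder comparison, with LOCF for missing data. It ties neither to the sample size.

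The parent plan (Combined protocol and SAP, Section 12.1) is more complete for missed working days: "The correlation between baseline and follow-up report is estimated with" r = 0.5, and the calculation is made "at the 0.05 significance level (two-sided) with a power of 0.80". Section 12.4 of that document sets a two-sided 5% level for inferential statistics, which can reasonably be carried over to AGIL-CV.

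**The concern.** The standardised differences are 10/18 = 0.556 for systolic and 5/11 = 0.455 for diastolic pressure. At the same alpha and beta, the smaller one needs markedly more patients, yet the two Ns differ by only 8. The missing details cannot explain this if they are common to both pressures, because they cancel from the ratio.

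At stake is whether the 5% beta is a real property of the plan. Section 1.9 carries these Ns forward through 50% discontinuation to 300, and then declares 300 adequate for the primary questions in general. Whether that holds depends on which comparison the Ns describe, and the reader cannot tell.

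**Working it through.** **Inputs.** From Section 1.9: alpha 0.05, power 0.95, systolic difference 10 and SD 18, diastolic difference 5 and SD 11, about 50% discontinuation by Month 60, 300 enrolled, hence 300 × 0.5 = 150 expected. From Section 12.4 of the parent plan: two-sided. Assumed, because the documents do not give it: the blood pressure correlation r. Results below use the noncentral t distribution unless marked otherwise.

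**1. Trying to reproduce the stated figures.** With k = (1.960 + 1.645)² = 12.99:

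| Setting | Formula (normal approximation) | Systolic N | Diastolic N |
|---|---|---|---|
| Paired change, r = 0 | k × 2(1−r) × (SD/difference)² | 87 | 128 |
| Paired change, r = 0.5 | same | 45 | 65 |
| Two equal groups, unadjusted, total | 4k × (SD/difference)² | 172 | 254 |
| Two equal groups, baseline-adjusted, r = 0.5, total | 4k(1−r²) × (SD/difference)² | 130 | 192 |
| Stated in Section 1.9 | not given | 128 | 136 |

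No row gives both stated figures. The systolic 128 alone can be matched: baseline-adjusted at r = 0.5, the normal approximation gives 2 × 12.99 × 0.75 × 3.24 = 63.2, so 64 per group and 128 in total. The same formula for diastolic gives 2 × 12.99 × 0.75 × 4.84 = 94.3, so 95 per group and 190 in total, not 136.

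**2. The ratio.** Every formula above has the form (constant) × (SD/difference)². With one test and one r, the constant cancels:

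- systolic (18/10)² = 3.24; diastolic (11/5)² = 4.84
- required ratio 4.84/3.24 = 1.49
- stated ratio 136/128 = 1.06

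**3. What each figure implies for the other.** 128 × 1.494 = 191.2, so about 192 diastolic. 136/1.494 = 91.0, so about 92 systolic.

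**4. Power.** Fix r so that 128 gives exactly 95% systolic power, then compute diastolic power at 136. The answer is 86.0% for a paired test and for two-group tests alike, that is, a beta of about 14%. By normal approximation: 3.605 × √(1.0625/1.494) − 1.960 = 1.08, and Φ(1.08) = 0.86.

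**5. Rounding.** If the SDs were rounded to whole numbers, the most favourable pair is 18.5 and 10.5: (10.5/5)²/(18.5/10)² = 4.41/3.42 = 1.29. This is still well above 1.06.

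**6. Correlations that would make each stated N exact** (two-sided, 95% power):

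| Test | r for systolic 128 | r for diastolic 136 |
|---|---|---|
| Two-group, baseline-adjusted | 0.50 | 0.68 |
| Two-group, change score | 0.63 | 0.73 |
| Paired change | −0.50 | −0.07 |

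The paired reading needs negative correlations between a patient's own baseline and follow-up pressure.

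**7. Effect on 300.** For within-patient change, 150 patients at Month 60 give 99.8% systolic and 97.4% diastolic power even at r = 0. For a baseline-adjusted two-group comparison at an assumed r = 0.5, the 192 needed for diastolic exceeds 150 (192/0.5 = 384 enrolled). With 150 split 75:75, diastolic power is 89%.

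**The case against.** The strongest reply is that the equal correlation is an assumption made here and not in the plan. Two pressures can have different correlations. For a change score the gap needed is only 0.63 against 0.73, and with favourable SD rounding about 0.65 against 0.71. The inputs come from a cited study that cannot be consulted here. This stands as far as it goes: a reader might infer that the two Ns are impossible, and the documents do not support that. They support a narrower statement, that the Ns do not share a basis unless pressure-specific correlations or tests were used, and no section gives any.

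Three other points are fair.

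- The 86% is approximate: about 87% one-sided, and 81% to 91% over the range of SD rounding.
- Sidedness is not really missing, since Section 12.4 of the parent plan sets it.
- That section also calls the analyses exploratory. This lowers what hangs on exact power, but does not make two explicit Ns at a stated beta agree.

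A reader might also infer that the responder comparison is underpowered or that 300 is too few. Neither is established. Section 1.9 does not say that 5 or 10 mmHg is the difference sought between responders and nonresponders. The correlation and the responder split are unknown. The number analysed at Month 60 may exceed 150, because Section 1.10 uses LOCF and Table 1 defines the last column as Month 60 or last visit.

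**Conclusion.** The point holds as an inconsistency in the reported calculation. Under one test and one correlation, the stated inputs require a ratio of 1.49 (no lower than 1.29 after SD rounding), and Section 1.9 reports 1.06. At least one N is therefore wrong, or rests on correlations or tests that differ between the pressures and are not disclosed. It cannot be shown which. That 128 fits one plausible setting might tempt a reader to blame 136, but nothing in the documents says that setting was used.

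The consequence depends on the unstated comparison. For within-patient blood pressure change, 300 enrolled and 150 remaining are enough at 5% beta at any r from 0 upwards. For two-group totals, 5% beta for the diastolic difference is not shown. At the assumed r = 0.5 with equal groups and 150 patients it would be about 11% (power 89%). The general claim that 300 is sufficient is thus broader than the calculation supports. This should be corrected, but it does not call for a different enrolment target.

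**What to change.** In Section 1.9, name one two-sided test, state whether it compares a patient with his or her own baseline or two groups, give the assumed correlation for each pressure, and recompute both Ns from that setting.

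- **If the Ns are for within-patient change:** for example, *paired t-test, two-sided 5%, 95% power: 45 (systolic) and 65 (diastolic) at an assumed baseline to follow-up correlation of 0.5; 87 and 128 at a correlation of 0.* The 150 patients expected at Month 60 suffice, and 300 stands.
- **If they are two-group totals:** give both from one setting, for example 130 and 192 (baseline-adjusted, assumed r = 0.5, 1:1). Because 192 exceeds 150, keep 300 and state the lower diastolic power (about 89% with 150 at 75:75) instead of a 5% beta.
- **If different correlations were used for the two pressures:** state them. One sentence then settles the arithmetic.

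In each case, limit the sufficiency claim at 5% beta to within-patient blood pressure change, unless the same calculation is shown for the DAS28 responder comparison, with its model, split and the handling of LOCF values. Power ranges built on a guessed correlation and split should not be written into the plan. Bring Section 1.4 into line.

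The cost is wording only, with no extra patients or data. The downside is that the power stated for the responder comparison becomes less favourable or is no longer claimed.

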12.4 Level of Significance

Inferential statistics will be performed at a nominal level of significance of 0.05 (two-sided). Due to the exploratory character of the analyses, the resulting p-values will not be adjusted for multiple testing.

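### Section 1.9 calls N=300 sufficient for all AGIL-CV primary questions at 5% beta, but its calculation supports this only for within-patient blood pressure change, not for the responder comparison

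*Protocol*

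**What the plan says.** Protocol (AGIL-CV), section 1.3, names three primary questions: change from baseline at Months 12, 24 and 60 in metabolic laboratory values, vital signs and body measurements; "The comparison between DAS28 responders and DAS28 nonresponders in terms of the primary parameters" (laboratory values and vital signs, so blood pressure is included); and "Determination of the time point and frequency of cardiovascular events in the course of the entire documentation".

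Section 1.9 opens with "Assuming an alpha and beta error of 5% each" and gives two results for Months 12, 24 and 60: "N=128 patients are required in order to detect a mean systolic blood pressure difference of 10 mmHg" (SD 18 mmHg) and "N=136 patients are required in order to detect a mean diastolic blood pressure difference of 5 mmHg" (SD 11 mmHg). It does not say whether the difference is within patients or between groups, and it gives no responder split, correlation or event rate. After allowing for about 50% discontinuation by Month 60 it concludes that "an overall number of N=300 patients is sufficient to address the primary research questions given the above-named estimations". Section 1.4 repeats the 300.

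Section 1.10 tests responders against nonresponders with a general linear model and fills missing data by LOCF. Section 12.3 of the combined protocol and SAP (the main AGIL plan) analyses observed cases, with a complete-data analysis in addition.

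**The concern.** The sufficiency statement is unqualified and covers every primary question, while nothing in the calculation is identified as the two-group comparison. Dividing about 150 patients into responders and nonresponders is more demanding than testing a mean change in all of them. If the report relies on the stated 5% beta, a non-significant diastolic responder comparison at Month 60 could be given more weight as evidence of no association than the data allow.

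**Working it through.** **Inputs.** From 1.9: differences of 10 and 5 mmHg, SDs of 18 and 11 mmHg, alpha and beta 0.05, 300 enrolled, about 50% discontinued, hence 300 × 0.5 = 150 at Month 60. Two-sided testing comes from section 12.4 of the main plan: "Inferential statistics will be performed at a nominal level of significance of 0.05 (two-sided". Assumed, because the documents give no figure: responder splits from 30:70 to 50:50, and baseline correlations r of 0.3, 0.5 and 0.7. Power is from the noncentral t distribution; sample sizes use the normal approximation.

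**1. The plan's own figures.** With (1.960 + 1.645)² = 12.99:
- Two equal groups, per group n = 2 × 12.99 × SD²/δ²: 85 systolic (170 in total) and 126 diastolic (252 in total).
- One sample with SD of change equal to the printed SD (r = 0.5), n = 12.99 × SD²/δ²: 43 and 63.

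Neither gives 128 and 136, and no single formula of this kind can: the inputs imply a diastolic-to-systolic ratio of (121/25)/(324/100) = 1.49, against 136/128 = 1.06. The attrition step is consistent: 136/0.5 = 272, below 300.

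**2. Within-patient change.** SD of change = SD × √(2(1−r)). The least favourable non-negative correlation is r = 0, giving SDs of 15.6 (diastolic) and 25.5 (systolic). Power is then 96% for 5 mmHg with 136 patients and 99% for 10 mmHg with 128. The claim stands here.

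**3. Responder comparison, 150 observed patients at Month 60.** The standard error is SD × √(1/n₁ + 1/n₂). For diastolic pressure at 75:75 it is 11 × √(2/75) = 1.80; at 45:105 it is 11 × √(1/45 + 1/105) = 1.96.

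| Analysed variable | SD (mmHg) | 75:75 | 45:105 |
|---|---|---|---|
| Systolic, 10 mmHg | 18 | 92% | 87% |
| Diastolic, 5 mmHg | 11 | 79% | 72% |
| Diastolic change, r = 0.3 | 11 × √1.4 = 13.0 | 65% | 57% |
| Diastolic change, r = 0.7 | 11 × √0.6 = 8.5 | 95% | 91% |
| Diastolic, baseline-adjusted, r = 0.5 | 11 × √0.75 = 9.5 | 89% | 83% |

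The second row also applies to change scores at r = 0.5, where the SD of change equals 11.

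**4. Reading 128 and 136 as two-group totals.** Equal groups give 88% systolic (64:64) and 75% diastolic (68:68), not 95%. Read as per-group numbers, 136 means 272 patients at Month 60 and 272/0.5 = 544 enrolled.

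**5. What 95% diastolic power needs.** N = 12.99 × (121/25)/(p(1−p)): 252 patients at Month 60 for p = 0.5 and 300 for p = 0.3, that is 504 to 600 enrolled. With 150 patients, the difference detectable at 95% power is 3.605 × 1.80 ≈ 6.5 mmHg for equal groups and 3.605 × 1.96 ≈ 7.1 mmHg at 30:70.

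**6. LOCF on all 300.** At SD 11, nominal diastolic power is 98% (150:150) to 95% (90:210). For change scores with r = 0.3 it is 91% to 86%.

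**The case against.** The strongest reply is that section 1.10 prescribes LOCF in the same paragraph as the responder test. Up to 300 patients could then enter at Month 60, with nominal diastolic power of 95-98%. The arithmetic is right, so 72-79% cannot be given as the power of the planned test without conditions. It does not rescue 1.9, however. That section sets minimum numbers at each time point and enlarges the sample for discontinuation, which is a count of patients still observed. The LOCF power depends on carried-forward values, and the main plan's observed-cases rule points the other way.

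Second, a general linear model may adjust for baseline. Section 1.10 lists no covariates, so adjustment is neither stated nor excluded. At r = 0.5 it would raise diastolic power to 83-89%. This stands as a reason to show a range.

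Third, Month 60 is the worst time point. If attrition is linear, about 270 and 240 patients remain at Months 12 and 24, and diastolic power at SD 11 is 93-96% and 90-94%. This also stands in part. But the tested responder definition requires the DAS28 criterion at 5 of 7 visits, and only three follow-up visits have occurred by Month 12 and four by Month 24. Of the three analysis points, only Month 60 can meet that definition.

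Two stronger readings are tempting and should not be made. A reader might infer that the true miss rate is several times 5% throughout. That holds only for diastolic pressure under the assumptions above: 21-28% at SD 11, against 8-13% for systolic and 5-9% for diastolic change at r = 0.7. A reader might also infer that the event question is underpowered. It asks for timing and frequency, which is estimation, so beta error does not apply; 1.9 attaches its 5% beta only to the blood pressure differences.

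**Conclusion.** The sufficiency statement is wider than the calculation behind it. It is supported for within-patient blood pressure change and not shown for the responder comparison. On the plan's own attrition figure, that comparison has about 72-79% diastolic and 87-92% systolic power at Month 60. This rests on observed cases only, a 30:70 to 50:50 split, two-sided 0.05, and SDs of 11 and 18 mmHg for the analysed variable. The documents supply neither the split nor the SD of change, so these are conditional figures. The main plan calls its analyses exploratory, which limits the consequence, but the stated beta is a figure readers will rely on and it should be corrected.

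**What to change.** - In 1.9 and 1.4, limit the sufficiency statement to within-patient blood pressure change, and say that this is the comparison sized.
- Add the power or detectable difference for the responder comparison, with the assumed split, SD of the analysed variable, any baseline adjustment, and analysis set. On 150 patients at 95% power and SD 11, that is about 6.5 mmHg diastolic with equal groups or 7.1 at 30:70.
- Reconcile LOCF in 1.10 with the observed-cases rule in section 12.3 of the main plan, and state which set the power refers to.
- Describe the cardiovascular event question as descriptive estimation not covered by the sample size calculation.

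The cost is wording and a short calculation. No extra patients are needed; the only downside is a less favourable stated power for the responder comparison.
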